Samples will be obtained at a minimum for the clinical laboratory tests outlined in [Table 2](#) at the visits indicated in [Appendix C](#) and [Appendix D](#).

Blood samples for serum chemistry tests should be collected following a minimum 8-hour fast prior to study drug intake (with the exception of the Screening Visit, which may be non-fasting). Subjects whose visits occur prior to the morning dose of study drug should

be instructed to fast after midnight until the blood sample is collected in the morning and thereafter take their study medications with food. Subjects whose visits occur following the morning dose of study drug should be instructed to fast after breakfast until the study visit occurs. At the Study Day 1 visit, a fasting blood sample should be collected prior to the first dose of study drug. Blood samples should still be drawn if the subject did not fast for at least 8 hours. Fasting or non-fasting status will be recorded in the source documents and on the laboratory requisition. The baseline laboratory test results for clinical assessment for a particular test will be defined as the last measurement prior to the initial dose of study drug.

A central laboratory will be utilized to process and provide results for the clinical laboratory tests.

Instructions regarding the collection, processing, and shipping of these samples will be provided by the central laboratory chosen for this study. The certified laboratory chosen for this study is Covance. Samples will be sent to the following addresses:

Covance
[name]
[name]
(For sites in North America)

Covance
[name]
[name]
[name]
(For sites in Europe, Russia and South Africa)

Covance (Asia) Pte Ltd
[name]
[name]
[name]
(For sites in Asia Pacific)

Table 2. Clinical Laboratory Tests

Hematology	Clinical Chemistry	Other Tests
Hematocrit	Blood Urea Nitrogen (BUN)	HBsAg ^e
Hemoglobin	Creatinine	Anti-HCV Ab ^e
Red Blood Cell (RBC) count	Total bilirubin ^{a,b}	HIV Ab ^e
White Blood Cell (WBC) count	Direct and indirect bilirubin	Urine and Serum
Neutrophils	Alanine transaminase	Human Chorionic
Bands, if detected	(SGPT/ALT)	Gonadotropin (hCG)
Lymphocytes	Aspartate transaminase	for females ^f
Monocytes	(SGOT/AST)	HCV RNA
Basophils	Alkaline phosphatase	Hepatitis B Panel ^g
Eosinophils	Sodium	Hemoglobin A1C ^e
Platelet count (estimate not acceptable)	Potassium	IL28B ^d

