- Baseline platelet count (< 90 or $\geq 90 \times 10^9/L$);
- Baseline albumin (< 35 or ≥ 35 g/L);
- Baseline creatinine clearance (< 60 , ≥ 60 to < 90 , ≥ 90 mL/min);
- Baseline eGFR (< 90 , ≥ 90 mL/min/1.73 m²);
- History of diabetes (yes/no);
- History of bleeding disorders (yes/no);
- History of depression or bipolar disorder (yes/no);

- History of cardiovascular disease (yes/no);
- Baseline metabolic syndrome (yes/no);
- Injection drug use (yes, within last 12 months; yes, more than 12 months ago; or no);
- Use of stable opiate substitution (yes/no);
- Concomitant use of Proton Pump Inhibitors (PPIs) (yes/no);
- Tobacco use (current, former, never, or unknown);
- Alcohol use (current, former, never, or unknown).

In addition, for cirrhotic subjects, the following will be summarized:

- Baseline Child-Pugh score (5, 6, or > 6).

Summaries of baseline resistance are described in Section 10.8.

For treatment-experienced subjects, any regimen that contains SOF with or without IFN or RBV is SOF-based. Otherwise, any regimen that contains IFN with or without RBV is IFN-based.

Any concomitant medication coded to the WHO Drug Dictionary ATC code of A02BC will be counted as a PPI.

If the IL28B genotype result is not available from a sample collected during the Screening period, then a result available from a sample collected at any time during the study will be used to summarize IL28B genotype. IL28B rs12979860 will be resulted as C/C, C/T, or T/T by the central laboratory.

HOMA-IR is defined as $\text{fasting glucose (mmol/L)} \times \text{fasting insulin } (\mu\text{IU/mL}) \div 22.5$. Subjects who do not have concurrent fasting glucose and fasting insulin values at baseline will be excluded from the summary of baseline HOMA-IR.

Baseline fibrosis stage is defined for subjects with non-missing liver biopsy scores, FibroScan scores, or FibroTest scores. Only one score will be used to categorize each

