11.3 Analysis of Laboratory Data

Data collected from the central and local laboratories, including additional laboratory testing due to a serious AE, will be used in all analyses.

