11.3.2 Statistical Methods

The baseline value for clinical laboratory tests will be the last non-missing measurement on or before the day of the first dose of study drug. Values on Day 1 must also be before the time of first dose if time is available. The same baseline value will be used for changes to Treatment Period visits and changes to Post-Treatment Period visits.

Visit Values

For each laboratory parameter listed in Section 11.3.1, values at each visit (baseline and post-baseline, including applicable post-treatment visits) will be summarized with the

sample size, mean, standard deviation, minimum, median, and maximum. Figures presenting mean values over time will be produced.

Change from Baseline

For each laboratory parameter listed in Section 11.3.1, changes from baseline to each post-baseline visit, including applicable post-treatment visits, will be summarized with the sample size, baseline mean; visit mean; and change from baseline mean, standard deviation, minimum, median, and maximum.

Shift Tables

Individual changes in the laboratory parameters listed in Section 11.3.1 will be tabulated using shift tables. Laboratory data values will be categorized as low, normal, or high based on normal ranges of the laboratory used for each sample. Shift tables from baseline to minimum value and maximum value during the Treatment Period will be created. For each parameter, the shift tables will cross tabulate the frequency of subjects with baseline values below/within the normal range to maximum above the normal range and with baseline values within/above the normal range to minimum below the normal range.

Maximum Toxicity Grade

The laboratory parameters listed in Table 9 will be assigned a toxicity grade of 1, 2, 3, or 4. The number and percentage of subjects with a maximum toxicity grade of 1, 2, 3 or 4 during the Treatment Period will be tabulated. To be counted, the post-baseline value must have a toxicity grade that is more extreme than the toxicity grade corresponding to the baseline value. For each laboratory parameter in Table 9, the summary will also include the number and percentage of subjects with a maximum of at least Grade 3. A listing of all relevant laboratory parameters will be provided for each subject who had an increase to Grade 2 or higher for any laboratory variable in Table 9.

Assessment of Hepatic Laboratory Values

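### SAP laboratory summaries ignore recorded fasting status, so on-treatment rises in glucose and triglycerides may partly reflect a change in fasting state (minor)

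*SAP*

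**What the plan says.** **Sampling (Protocol 5.3.1.1, Clinical Laboratory Tests).** The general rule is "Blood samples for serum chemistry tests should be collected following a minimum 8-hour fast prior to study drug intake"; only the Screening sample is exempt. The Day 1 sample is to be fasting and taken before the first dose. For later visits there are two cases. Subjects seen before the morning dose should "be instructed to fast after midnight until the blood sample is collected in the morning". For the others, "Subjects whose visits occur following the morning dose of study drug should be instructed to fast after breakfast until the study visit occurs"; study drug is taken with food (Protocol 5.5.4). In every case, "Blood samples should still be drawn if the subject did not fast for at least 8 hours". Whether the sample was fasting is written in the source documents and on the laboratory requisition.

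**Analysis (SAP 11.3 to 11.3.2).** "Data collected from the central and local laboratories, including additional laboratory testing due to a serious AE, will be used in all analyses". Visit values, changes from baseline, shifts to the maximum and maximum grade all use these data with no condition on fasting. For grades, "To be counted, the post-baseline value must have a toxicity grade that is more extreme than the toxicity grade corresponding to the baseline value". Table 9 grades glucose from above the upper limit of normal (ULN), with Grade 2 starting above 8.9 mmol/L, and has no fasting qualifier. Cholesterol is graded too. Triglycerides are summarised but not graded.

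**Elsewhere in the SAP.** Fasting does matter for baseline HOMA-IR (SAP 7.1): "Subjects who do not have concurrent fasting glucose and fasting insulin values at baseline will be excluded". SAP Table 6 also uses fasting glucose to define metabolic syndrome.

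**The concern.** A change from baseline is interpretable only if the sampling condition is the same at both ends. Here it can differ by design: baseline should be fasting and before any dose, whereas an on-treatment sample may follow a meal taken with the dose. Grades and high shifts use the most extreme value over the Treatment Period, so a single fed sample among several can create a new Grade 1.

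Nothing else in the plan removes the effect. There is no control arm, arms are set by cirrhosis status (Protocol 8.3), and SAP 11.1 reports safety only for the pooled population. A reader of the safety tables could attribute a meal-related rise in glucose or triglycerides to the drug. Safety is part of the primary objective (Protocol 4.1), although no glycaemic or lipid outcome is named there.

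**Working it through.** The documents give no figure for fasting status or for meal-related shifts, so there is no plan figure to reproduce. The check has two parts.

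**1. Which analytes can be affected.** This sets the sampling schedule (Protocol Table 2, Appendices C and D) beside the analysis (SAP 11.3.1 and Table 9).

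| Analyte | On-treatment sample | Graded | Exposed |
|---|---|---|---|
| Glucose | Weeks 1, 2, 4, 8 (and 12 in Arm B) | Yes | Means, high shifts, grade |
| Triglycerides | Same | No | Means, high shifts |
| Total cholesterol | Same | Yes | Same route; presumably smaller effect |
| Total insulin | None (Day 1 and Post-Treatment Week 12 only) | No | Not on treatment |
| LDL, HDL | None (baseline only) | No | No |

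There are thus 4 scheduled on-treatment chemistry draws in Arm A and 5 in Arm B.

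**2. Possible size for glucose (illustration; every input is assumed).** Inputs: fasting subject means average 5.2 mmol/L with between-subject SD 0.45; within-subject SD 0.3; 4 draws; no drug effect; meal rise D of 0.5 to 1.0 mmol/L; non-fasting share on treatment f_t of 10% to 30%; non-fasting share at baseline f_b of 0.

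*Mean change.* Bias = (f_t − f_b) × D.
- Low end: (0.10 − 0) × 0.5 = +0.05 mmol/L.
- High end: (0.30 − 0) × 1.0 = +0.30 mmol/L.
- Reversed case, f_b = 10% and f_t = 0: (0 − 0.10) × 0.5 = −0.05, and (0 − 0.10) × 1.0 = −0.10 mmol/L.

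*New value above ULN.* This is the share of all subjects with baseline at or below ULN and at least one of 4 on-treatment values above it, by simulation of 1,000,000 subjects.

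| ULN (assumed) | All fasting | f_t = 10%, D = 0.5 | f_t = 30%, D = 1.0 |
|---|---|---|---|
| 6.1 mmol/L | 8.4% | about 13% | about 47% |
| 5.6 mmol/L | 22.8% | about 29% | about 56.5% |

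No simulated subject with a baseline at or below ULN reached Grade 2 (above 8.9 mmol/L).

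*Second input set* (mean 5.1, between-subject SD 0.4, within-subject SD 0.3, ULN 6.1, 4 draws, D of 0.5 to 2 mmol/L). The share is 5.0% with all draws fasting, 9.0% to 36.3% at f_t = 10%, and 14.3% to 67.1% at f_t = 25%. Grade 2 or higher stays at or below 0.01% throughout. Subjects with diabetes were not modelled in either set.

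**The case against.** The strongest reply is that the protocol already has a fasting rule. The 8-hour minimum covers every visit except Screening, so non-fasting draws are tolerated exceptions or early post-dose visits. That is correct, and it means the non-fasting share could be small. It does not close the gap: visits after the morning dose are expressly provided for, the fast then runs only from breakfast, and a sample meets 8 hours only if the visit is at least that long after the meal.

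A second reply is that these are descriptive tables in a study with no hypothesis tests (SAP 10.2). The SAP's adverse events and laboratory abnormalities of interest are hepatic (or, for adverse events, hepatocellular carcinoma). This stands, and it limits the severity.

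A third is that restricting safety tables to fasting samples would discard safety data and, if applied to some grades only, mix data sources within one table. This also stands, and is why the fasting-only summaries should be added and not substituted.

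A reader might infer more than the documents support:
- *That the bias must be upward.* Day 1 blood is also drawn if the fast failed, and a Screening value, which may be non-fasting, becomes baseline if Day 1 is missing. Upward is the likelier direction, not a certain one.
- *That on-treatment insulin or lipids in general are distorted.* Insulin has no on-treatment sample. LDL and HDL have no post-baseline sample.
- *That spurious Grade 2 hyperglycaemia will appear.* The illustrations show essentially none in subjects without diabetes.

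**Conclusion.** The concern holds in limited form. The protocol lets fasting state differ between baseline and treatment, and the SAP does not use the recorded status to separate the two. Mean changes and high shifts in glucose and triglycerides, to a lesser extent cholesterol, and new Grade 1 glucose can therefore partly reflect fasting state.

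The size cannot be derived from the documents. The range of about 8% rising to 13–47% rests wholly on the assumed glucose distribution, ULN, meal rise and non-fasting share. It shows that the effect could be large enough to mislead, not that it will occur. That cholesterol is less affected is likewise an assumption. Grade 2 or higher glucose is not shown to be affected, and SVR12 is untouched. Severity is minor.

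**What to change.** In SAP 11.3.2, keep the all-sample safety tables as they are. Add, for glucose, triglycerides and cholesterol, summaries of visit values, change from baseline, high shifts and (where graded) maximum grade, restricted to samples recorded as fasting at both baseline and the visit. State that any comment on a drug effect on these analytes will rest on those summaries. Flag non-fasting values in the listings.

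In Protocol 5.3.1.1, reconcile the 8-hour minimum with the instruction that the fast runs from breakfast when the visit follows the morning dose.

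The cost is a short SAP addition and one extra set of tables. Fasting status is already recorded in source and on the requisition, and the HOMA-IR rule presupposes that it reaches the analysis data; that should be confirmed. What is recorded is fasting or non-fasting, not hours fasted, so the restriction should use that status. The downside is fewer values in the added tables, including the loss from them of any subject whose baseline sample was non-fasting. No safety data leave the main tables.

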In both Studies M14-867 and M14-868, in all subjects with baseline alanine aminotransferase (ALT) elevations, the ALT levels showed a trend toward normal or became normal with DAA treatment. There have been no on-treatment ALT elevations above baseline. The ALT normalization pattern was similar across all arms (i.e., all GLE and PIB dose levels) in both studies. Other laboratory abnormalities were infrequent and primarily associated with the well-described hemolytic effect of RBV, manifesting as Grade 1 anemia in a total of 4 subjects, all occurring in Study M14 868 RBV-containing arms. Observed total bilirubin elevations were Grade 1 or 2 with predominantly indirect fraction, were mostly isolated occurrences, and normalized or stabilized with continued DAA therapy. Total bilirubin elevations were primarily observed in the RBV-containing arms.

The safety of the combination regimen of GLE and PIB in subjects with compensated cirrhosis is investigated in Study M14-867 Part 2 (GLE/PIB [200 mg/120 mg] QD for 12 weeks) and Study M14-868 Part 2 (GLE/PIB [300 mg/120 mg] QD for 12 weeks with and without ribavirin or for 16 weeks without ribavirin. Based on 82 subjects with compensated cirrhosis enrolled in these arms who have received 4 weeks or more of treatment, the GLE and PIB regimen has demonstrated a favorable safety profile in this patient population. The majority of adverse events have been Grade 1 or 2 and there have been no treatment discontinuations.

A detailed discussion of the preclinical pharmacology and toxicology, in vitro virology and metabolism, and clinical data for GLE, PIB, and the combination of GLE and PIB can be found in the GLE and PIB Fixed-Dose Combination Investigator's Brochure.¹⁰

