8.1.5.2 Clinical Laboratory Data

Clinical laboratory tests will be summarized at each visit. The baseline value will be the last non-missing measurement prior to the initial dose of study drug. Mean changes from baseline to each post-baseline visit, including Final Treatment Visit, will be summarized descriptively. Changes from baseline to post-baseline in the CTCAE grading of laboratory values will also be summarized.

Laboratory data values will be categorized as low, normal, or high based on reference ranges of the laboratory used in this study. The number and percentage of subjects who experience post-baseline shifts during treatment in clinical laboratory values from low/normal to high and high/normal to low based on the normal range will be summarized.

In addition, the number and percentage of subjects with post-baseline values meeting pre-specified criteria for Potentially Clinically Significant laboratory values or toxicity grades during treatment will be summarized.

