The number and percentage of subjects with laboratory values meeting the following criteria during treatment will be summarized:

- Post-nadir (preceding value is lower than the subsequent value) ALT $> 5 \times \text{ULN}$ (regardless of grade change);
- Total bilirubin $\geq 2 \times \text{ULN}$ and $>$ baseline (i.e., a post-baseline value must be more extreme than the baseline value to be considered);
- Post-nadir ALT $> 3 \times \text{ULN}$ and total bilirubin $> 2 \times \text{ULN}$;
- Post-nadir ALT $> 3 \times \text{ULN}$ and total bilirubin $\leq 2 \times \text{ULN}$.

Four listings (one for each bullet above) of all hepatic laboratory values including ALT, AST, total, indirect and direct bilirubin, ratio of direct to total bilirubin, and alkaline phosphatase values will be provided for each subject who met the criterion defined above.

Hepatic Laboratory Abnormalities of Interest

Among the events assessed under "Assessment of Hepatic Laboratory Values," the following criteria are of interest:

- Confirmed post-nadir ALT $> 5 \times \text{ULN}$;
- Post-nadir ALT $> 3 \times \text{ULN}$ and a concurrent total bilirubin $> 2 \times \text{ULN}$ with a direct/total bilirubin ratio > 0.4 .

To support the assessment of hepatic laboratory abnormalities of interest, the following potential events will be summarized:

- Confirmed post-nadir ALT $> 5 \times \text{ULN}$;
- Post-nadir ALT $> 3 \times \text{ULN}$ and total bilirubin $> 2 \times \text{ULN}$ and direct/total bilirubin ratio > 0.4 .

Two listings (one for each bullet) of all hepatic laboratory values including ALT, AST, total, indirect and direct bilirubin, ratio of direct to total bilirubin, and alkaline phosphatase values will be provided for each subject who met the criterion defined above.

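### SAP 11.3.2 counts a laboratory grade only above the baseline grade and shows no baseline grade, so an AST rebound within a raised baseline grade enters no frequency table; the narrowing from the protocol is not logged

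*SAP*

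**What the plan says.** Protocol 8.1.5.2 makes two commitments on laboratory grades. The first reads "Changes from baseline to post-baseline in the CTCAE grading of laboratory values will also be summarized", and the synopsis repeats it. The second promises the number and percentage of subjects meeting pre-specified criteria for potentially clinically significant values or grades. It ends "toxicity grades during treatment will be summarized" and sets no condition relative to the baseline grade.

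SAP 11.3.2, under Maximum Toxicity Grade, answers both with one table: "The number and percentage of subjects with a maximum toxicity grade of 1, 2, 3 or 4 during the Treatment Period will be tabulated", plus a row for at least Grade 3. The condition for being counted is that "the post-baseline value must have a toxicity grade that is more extreme than the toxicity grade corresponding to the baseline value". The baseline grade is not part of the display. A listing is added "for each subject who had an increase to Grade 2 or higher for any laboratory variable in Table 9".

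Two other parts of SAP 11.3.2 bear on this:

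- The shift tables use low, normal and high. For a high maximum they take only subjects "with baseline values below/within the normal range to maximum above the normal range".
- The hepatic assessments count post-nadir ALT above 5 x ULN, "regardless of grade change", and post-nadir ALT above 3 x ULN with bilirubin either above or not above 2 x ULN. The nadir (the last value before the first increase, baseline included) is defined for ALT only.

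On the population, Protocol 5.6.3 describes AST and ALT as raised in chronic HCV infection, and Protocol 5.2.2 criterion 9 excludes AST only above 10 x ULN. Protocol 3.0 reports that in two earlier studies, "in all subjects with baseline alanine aminotransferase (ALT) elevations, the ALT levels showed a trend toward normal or became normal with DAA treatment".

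**The concern.** When a liver enzyme starts high because of the infection and falls once treatment begins, the pre-treatment grade is a poor yardstick for injury on treatment. A subject can normalise and then rise steeply without passing the starting grade. The SAP recognises this for ALT by adding counts that ignore grade change. It does not do so for AST.

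The display loses information too. A move from Grade 0 to 3 and a move from Grade 2 to 3 land in the same cell. A subject who was abnormal at baseline and no worse later cannot be told apart from one who was never abnormal.

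Safety is a primary objective (Protocol 4.1). As written, the grade table could show no Grade 3 AST for a subject whose AST normalised and then rose to just under 20 x ULN.

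**Working it through.** The plan states no figure on this point, so there is none to reproduce. The check applies the SAP's counting rules to example courses.

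**Inputs.** AST grades from SAP Table 9: Grade 1 is above 1 and up to 3 x ULN, Grade 2 up to 5, Grade 3 up to 20, Grade 4 above 20. The entry limit for AST is 10 x ULN at Screening, so a Grade 3 baseline is possible.

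**Rules.**
- Grade table: counted if post-baseline grade > baseline grade.
- Shift table (high): counted if baseline ≤ ULN and maximum > ULN.
- ALT-type rule, if it were applied to AST: counted if a value is > 5 x ULN and above the first nadir, baseline included.

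**AST courses (x ULN; illustrative).**

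| Baseline → low → later | Grades | Grade table | Shift table | ALT-type rule |
|---|---|---|---|---|
| 2 → 0.8 → 2.5 | 1 → 0 → 1 | no | no | no |
| 4 → 0.8 → 4.5 | 2 → 0 → 2 | no | no | no |
| 4 → 0.8 → 5.5 | 2 → 0 → 3 | yes | no | yes |
| 6 → 0.8 → 6 | 3 → 0 → 3 | no | no | yes |
| 9 → 0.8 → 19 | 3 → 0 → 3 | no | no | yes |
| 6 → 0.8 → 20.5 | 3 → 0 → 4 | yes | no | yes |

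In the fifth row the rise from the low point is 19/0.8 = 23.75-fold, and the peak is 19/9 = 2.1 times baseline. It enters neither the grade table nor the shift table. The listing of increases to Grade 2 or higher does not pick it up either, because the grade did not increase over baseline.

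**Ceiling of the uncounted rebound.** It is the upper limit of the baseline grade: 3 x ULN from Grade 1, 5 x ULN from Grade 2, 20 x ULN from Grade 3.

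**Cells of a full table.** With baseline and worst grade each running 0 to 4, there are 5 x 4 = 20 cells with an on-treatment grade of 1 to 4. The SAP rule counts the 4 + 3 + 2 + 1 = 10 cells with an increase. It omits 4 same-grade cells and 6 cells that are lower but still graded. For Grade 3 or higher it counts 7 of 10 cells. These are cells, not subjects.

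**Why the full table alone is not enough.** AST of 9 → 0.8 → 19 (rebound) and 9 → 6 → 0.8 (steady fall) both have baseline Grade 3 and worst on-treatment Grade 3, so they share a cell. The ALT-type rule separates them: the first rises from its nadir to above 5 x ULN, and the second never rises. Because that nadir includes baseline, the rule also counts 9 → 19 followed by a steady fall.

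**Protocol against SAP 12.1.** Item 10 logs the added hepatic methods and item 11 logs a reduced vital-sign summary. No item mentions the laboratory grade summaries.

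**The case against.** The strongest reply has four parts.

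- **The grade-change summary exists.** The protocol fixes no layout. A table conditioned on exceeding the baseline grade, with a listing of increases to Grade 2 or higher, is a summary of grade change in the worsening direction. This stands. A reader might infer that the protocol's summary is not produced at all, and the documents do not support that. What is missing is the starting grade, the unchanged and improved grades, and the count without a baseline condition. It can also be argued that the protocol left the criteria to be pre-specified and the SAP did so. That weakens the charge of departure, but a limit the protocol does not state still belongs in 12.1.
- **The values are visible elsewhere.** AST and GGT are in the visit-value and change-from-baseline summaries, which report a maximum, and the baseline distributions are summarised under SAP 7.1. For counted increases to Grade 2 or higher, the starting level can be looked up in the listing. This stands in part. The continuous summaries use one assessment per window (SAP 6.2), so an off-schedule peak can drop out. A return to exactly the baseline value shows a change of zero.
- **Liver safety is built around ALT.** The two bilirubin strata together capture post-nadir ALT above 3 x ULN, and AST and alkaline phosphatase are listed for those subjects. This stands, and it confines the gap to rebounds without such an ALT rise.
- **Adverse-event tables.** A significant rise may be reported as an adverse event. Under Protocol 6.1.1.1 that depends on discontinuation, intervention or the investigator's judgement, so it is not a systematic count.

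**Conclusion.** The point holds as a narrowing of the laboratory grade summaries that is not logged, with one specific blind spot. SAP 11.3.2 reduces two protocol commitments to an increase-only table without baseline grade. For AST, a rebound that stays within the baseline grade enters no frequency table, up to 20 x ULN when the baseline is Grade 3. The practical gap is AST-predominant rebound, and also GGT or alkaline phosphatase if these are raised at baseline.

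The number of subjects affected cannot be computed, because the documents give no baseline distribution of AST, GGT or alkaline phosphatase. Two further inferences should therefore be resisted:

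- That GGT is raised by HCV in this population. Protocol 5.6.3 names only AST and ALT, and the passage on falling levels in Protocol 3.0 concerns ALT only. That AST falls in the same way is an assumption here.
- That the tabulated percentages understate a particular rate among subjects still able to worsen. Without the baseline distribution there is no such denominator, and using all treated subjects is an ordinary choice.

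The efficacy analyses are untouched. The change is worth making because it uses data already collected and restores what Protocol 8.1.5.2 describes.

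**What to change.** In SAP 11.3.2:

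1. For every Table 9 test, tabulate baseline grade by worst on-treatment grade, and keep the existing increase-only count beside it. This shows the starting grade and gives the on-treatment grade count without a baseline condition. It also covers GGT and alkaline phosphatase.
2. For AST, add the number and percentage of subjects with a post-nadir value above 5 x ULN regardless of grade change, using the ALT nadir definition already in 11.3.2 (first nadir, including baseline).
3. In SAP 12.1, log any difference from Protocol 8.1.5.2 that remains, with the reason.

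The cost is one extra table and one extra row, with no new data. The AST row has two limits. It adds only subjects who start above 5 x ULN, since from a lower baseline such a value is already a grade increase; rebounds within Grade 1 or 2 will show only as unchanged grades in the new table. It will also count a small rise from a baseline already above 5 x ULN, so it should be read with the individual values.

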For the **assessments of hepatic laboratory values** and **hepatic laboratory abnormalities of potential interest**, the maximum ratio relative to the ULN will be used to determine if subjects meet any of the criteria listed above. The ALT and total bilirubin values do not need to be concurrent in order to meet the defined criteria in statistical summaries. For ALT, the post-baseline value must represent an increase from the first nadir (including baseline) to be counted. First nadir is defined as the last value prior to the first increase. For total bilirubin, a subject will be counted if the post-baseline laboratory value meets the above criteria regardless of the baseline laboratory value (i.e., the post-baseline laboratory value does not need to be worse than the baseline laboratory value), except where noted above. A confirmed post-nadir increase in ALT is defined as two consecutive values of $ALT > 5 \times ULN$ after nadir, either both during treatment or at the final treatment measurement and the next consecutive post-treatment measurement. A single post-nadir ALT value of greater than $5 \times ULN$ followed by lost to follow-up (no additional ALT values) also will be considered (i.e., will not require confirmation). The ratio of direct to total bilirubin will be calculated using the same date/time sample corresponding to the total bilirubin elevation.

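### SAP 11.3.2 plans no count of the concurrent ALT/bilirubin/direct-fraction event it names as of interest, and its screen for that event can drop a true case if the direct/total ratio is read at the bilirubin maximum

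*SAP*

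**What the plan says.** SAP 11.3.2 handles this signal in layers.

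- **Broad assessment.** Four criteria are counted and listed. One is post-nadir ALT > 3 x ULN with total bilirubin > 2 x ULN, with no condition on the direct fraction. The listing for each criterion shows all hepatic values, including the direct/total ratio.
- **Criteria of interest.** Among those events, the SAP singles out post-nadir ALT > 3 x ULN with "a concurrent total bilirubin" > 2 x ULN and a direct/total ratio > 0.4.
- **What is tabulated for that criterion.** "To support the assessment of hepatic laboratory abnormalities of interest, the following potential events will be summarized". The corresponding row has the same three thresholds but no longer asks for concurrency. Its listing covers only subjects who meet the row.

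Three derivation rules follow. First, "the maximum ratio relative to the ULN will be used to determine if subjects meet any of the criteria listed above". Second, "The ALT and total bilirubin values do not need to be concurrent in order to meet the defined criteria in statistical summaries". Third, "The ratio of direct to total bilirubin will be calculated using the same date/time sample corresponding to the total bilirubin elevation". The SAP also says that, except where noted, a post-baseline bilirubin counts whatever the baseline value was.

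**The concern.** The criterion of interest describes three findings in one sample. The planned row tests them on values that may come from different visits, and no other row counts the same-sample event.

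A looser row is acceptable as a screen if it contains every true case. Whether this one does depends on the third rule. The elevation it refers to could be the subject's maximum bilirubin or any sample above 2 x ULN. The maximum rule in the same paragraph points to the first, but the text does not settle it. Two programmers could follow it and report different counts.

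Safety is part of the primary objective. Up to about 16 of 80 subjects (16/80 = 20%) may have compensated cirrhosis, and SAP 11.1 pools safety across arms. The output is therefore one small count, in which a single subject is visible.

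**Working it through.** The documents give no figure for this criterion, so there is none to reproduce. The check codes the rules and runs constructed subjects through them.

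**Rules, all from SAP 11.3.2** (values as multiples of ULN; *r* = direct/total ratio; first nadir = last value before the first ALT increase, baseline included):

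1. Event of interest: some post-nadir date *i* has ALT_i > 3, TB_i > 2 and r_i > 0.4.
2. Broad row: max post-nadir ALT > 3 and max post-baseline TB > 2.
3. Potential event, maximum reading: rule 2 holds and r > 0.4 at the sample with maximum TB.
4. Potential event, any-sample reading: max post-nadir ALT > 3 and some post-baseline sample has TB > 2 with r > 0.4.

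**Constructed subjects** (baseline, Weeks 1, 2, 4, 8):

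| Subject | ALT | Total bilirubin | Direct/total |
|---|---|---|---|
| A | 1.5, 1.0, 0.9, 1.2, 4.0 | 0.8, 2.8, 1.5, 1.2, 2.3 | 0.3, 0.2, 0.2, 0.3, 0.6 |
| A′ | 1.5, 1.0, 4.0, 1.2, 1.0 | 0.8, 1.0, 2.3, 1.2, 2.8 | 0.3, 0.2, 0.6, 0.3, 0.2 |
| B | 1.5, 4.0, 1.0, 0.8, 0.7 | 0.8, 0.9, 1.0, 1.2, 2.4 | 0.3, 0.3, 0.3, 0.3, 0.5 |

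| Subject | 1. Event of interest | 2. Broad row | 3. Maximum reading | 4. Any-sample reading |
|---|---|---|---|---|
| A | yes | yes | **no** | yes |
| A′ | yes | yes | **no** | yes |
| B | no | yes | yes | yes |

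- **A:** at Week 8, ALT 4.0, bilirubin 2.3 and ratio 0.6 meet all three conditions. The maximum bilirubin is 2.8 at Week 1 with ratio 0.2, so the maximum reading drops the subject.
- **A′:** the same miss with the indirect peak after the event. The event is at Week 2 and the peak of 2.8 (ratio 0.2) is at Week 8.
- **B:** the ALT rise (Week 1) and the bilirubin rise (Week 8) never coincide, yet the subject is a potential event under both readings.

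**Why this is general.** If date *i* satisfies rule 1, then max post-nadir ALT ≥ ALT_i > 3 and max TB ≥ TB_i > 2, so rule 2 holds. Sample *i* itself satisfies the bilirubin part of rule 4, so rule 4 holds. Rule 3 need not hold, because the maximum TB may be at another date with r ≤ 0.4.

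**Check on 300,000 arbitrary random profiles.** This tests set logic only and does not estimate a rate. Of 19,421 profiles with the event of interest, the maximum reading missed 1,802, the any-sample reading missed 0, and 0 were absent from the broad row. The maximum reading counted 30,107 profiles without the event.

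**Could a bilirubin peak be indirect here?** Protocol 3.0 reports of earlier studies: "Observed total bilirubin elevations were Grade 1 or 2 with predominantly indirect fraction". SAP Table 9 Grade 2 runs to 3 x ULN, so it includes values above 2 x ULN such as A's 2.8. Protocol exclusion criterion 9 limits direct bilirubin at screening and sets no limit on total bilirubin. An indirect peak is therefore possible, but none of this gives its frequency.

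**The case against.** The strongest reply is that the SAP does this openly. It calls the tabulated rows potential events, says they support the assessment, and states that concurrency is not required. Counting subject B is thus a disclosed feature of a screen. A reader might infer that the plan presents this row as the event of interest itself and so reports a wrong number under that label. The text does not support that.

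A reader might also infer that a true case could vanish from the study output. It could not. Every true case meets the broad ALT > 3 and bilirubin > 2 x ULN criterion, which is counted and listed with the direct/total ratio. With few such subjects, the listing is easy to read.

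The miss also depends on one reading of the ratio rule; under the any-sample reading nothing is missed. And the support for an indirect peak is limited: Protocol 3.0 says that the elevations were mainly in ribavirin-containing arms and mostly isolated, and this trial has no ribavirin.

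All of that stands and limits the point. It does not supply the missing count or say which sample carries the ratio. Nor does it make the row a safe screen under the reading that its own paragraph favours.

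**Conclusion.** The point holds in a narrow form. No count of the concurrent event is planned, and the sample that carries the direct/total ratio is not clearly defined. If that sample is the bilirubin maximum, the potential-event row and its listing can omit a subject who had the event. If it is any sample above 2 x ULN, they cannot.

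One subject is 1/80 = 1.25% of the planned enrolment. The number of such events is not given; if 0 to 2 subjects in 80 is assumed, the rate lies between 0% and 2.5% (2/80), and one misclassified subject moves it by 1.25 percentage points. How often a miss would occur cannot be derived from the documents. Efficacy results are unaffected, and Protocol 8.2 plans no formal hypothesis test. This is a minor to moderate fix to a safety derivation.

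**What to change.** In SAP 11.3.2:

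1. Add a count of subjects with any on-treatment sample date on which post-nadir ALT > 3 x ULN, total bilirubin > 2 x ULN and direct/total ratio > 0.4 are all met, with the ratio taken from that same sample. Subjects A and A′ are then counted and B is not.
2. For the potential-event row, state that the ratio is evaluated at any bilirubin sample > 2 x ULN. The screen and its listing then contain every true case.
3. Keep the existing maximum-based ALT/bilirubin rows unchanged and label them as non-concurrent screens. The maximum rule should stay for these rows: without it, a subject with one high and one lower bilirubin could fall into both the > 2 and the ≤ 2 x ULN rows.

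The cost is a few sentences and one extra programmed row. The values are already collected. The thresholds stay as the SAP has them, and no clinical management rule changes.
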